8.5 Additional assessments

[figure not shown]

[figure not shown]

e

8.5.3 Biomarkers

[figure not shown]
At the screening the selection of patient in each cohort will be based on the mutational status of T315I during screening as mentioned in the visit schedule [Table 8-1](#). Patient's BCR-ABL1 mutation status needs to be available and results have to be done within 6 months of screening. In addition, mutational analysis will be performed at screening to confirm the historical T315I mutational record if available.

8.5.4 Imaging

Not Applicable

9 Study discontinuation and completion

9.1 Discontinuation and completion

9.1.1 Study treatment discontinuation and study discontinuation

Discontinuation of study treatment for a subject occurs when study treatment is stopped earlier than the protocol planned duration and can be initiated by either the subject or the investigator.

The investigator must discontinue study treatment for a given subject if, he/she believes that continuation would negatively impact the subject's well-being.

Patients who discontinue the study treatment for an adverse event suspected to be related to study drug or an abnormal laboratory value suspected to be related to study drug must be followed as described in [Section 8](#)

Patients may also be discontinued from the study treatment if any of the following occurs:

- discovery of patient ineligibility
- errors in treatment compliance [study treatment, other prescribed or non-prescribed medications]
- missed/unscheduled/off schedule/incomplete/incorrect assessments
- major protocol deviation
- use of prohibited treatment refer to [Section 15-Appendices](#)
- any other protocol deviation that results in a significant risk to the patient's safety

In addition to the general discontinuation criteria, the following study specific criteria will also require discontinuation of study treatment:

- In the event of detection of new T315I mutations during the study, the patient **must** be discontinued from the study treatment. The Novartis Managed Access Program (MAP) ABL001A02401M Cohort will be available for those patients without a reasonable alternative options if treating physician and patient still choose to pursue treatment with Asciminib.
- In the event of a pregnancy during study, if a patient wants to pursue the pregnancy then patient **must** be discontinued from the study treatment. However, in the event of a spontaneous miscarriage or in the event of elective abortion, the patient is permitted to continue study treatment.
- In the event of treatment failure the patient must be discontinued from the study treatment. The following events will constitute 'treatment failure', defining failure of a third line treatment:
 - No CHR at three months after initiation of therapy or thereafter
 - BCR-ABL1 ratio > 10% IS at 24 weeks after initiation of therapy or thereafter
 - BCR-ABL1 ratio > 1% IS at 48 weeks after initiation of therapy or thereafter
 - Loss of CHR, MR2 at any time after initiation of therapy

- Detection of new BCR-ABL1 mutations which potentially cause resistance to study treatment (asciminib) at any time after initiation of therapy
- Confirmed loss of MMR in 2 consecutive tests ([Section 8.5](#)) (BCR-ABL1 > 0.1%)
- In the event of disease progression the patient must be discontinued from the study treatment. The following events are considered disease progression.
 - CML-related death (any death during treatment or follow-up if the principal cause of death is marked as “study indication” in the eCRF by the investigator, or if the death occurred subsequent to documented progression to AP/BC and the cause of death is reported as “unknown” or not reported by the investigator).
 - Accelerated phase (AP) as defined by any of the following:
 - $\geq 15\%$ blasts in the peripheral blood or bone marrow aspirate, but $< 30\%$ blasts in the peripheral blood or bone marrow aspirate
 - $\geq 30\%$ blasts plus promyelocytes in peripheral blood or bone marrow aspirate
 - $\geq 20\%$ basophils in the peripheral blood
 - Thrombocytopenia ($< 100 \times 10^9/L$) that is unrelated to therapy
 - Blast crisis (BC) as defined by any of the following:
 - $\geq 30\%$ blasts in peripheral blood or bone marrow aspirate

If discontinuation of study treatment occurs, the investigator should make a reasonable effort to understand the primary reason for the subject’s premature discontinuation of study treatment and record this information.

Subjects who discontinue study treatment or who decide they do not wish to participate in the study further should NOT be considered withdrawn from the study UNLESS they withdraw their consent (see withdraw of informed consent section.). Where possible, they should return for the assessments indicated in the assessment schedule. If they fail to return for these assessments for unknown reasons, every effort (e.g. telephone, e-mail, letter) should be made to contact the subject/pre-designated contact as specified in the lost to follow-up section. This contact should preferably be done according to the study visit schedule.

If the subject cannot or is unwilling to attend any visit(s), the site staff should maintain regular telephone contact with the subject, or with a person pre-designated by the subject. This telephone contact should preferably be done according to the study visit schedule.

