| Study population | 
One hundred and fifteen (115) patients with CML-CP without T315I mutation who have had at least 2 prior TKIs (90 patients) and CML-CP harboring the T315I mutation (25 patients) with at least 1 prior TKI will be considered for the current study. Patients with a medical history of the T315I mutation at study entry will be included in the trial. Previous medical records should be used to confirm the patient's mutational status/history.
 |
| Key Inclusion criteria | 
Participants eligible for inclusion in this study must meet all of the following criteria:
 
 Written informed consent must be obtained and signed prior to participation in the study Male or female patients with a diagnosis of CML-CP ≥ 18 years of age Patients must meet all of the following laboratory values at the screening visit: 
 < 15% blasts in peripheral blood or bone marrow < 30% blasts plus promyelocytes in peripheral blood or bone marrow < 20% basophils in the peripheral blood ≥ 50 x 10⁹/L (≥ 50,000/ mm³) platelets Transient prior therapy related thrombocytopenia (< 50,000/mm³ for ≤ 30 days prior to screening) is acceptable |

| | |
|--|--|

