One hundred and fifteen (115) patients with CML-CP without T315I mutation who have had at least 2 prior TKIs and CML-CP harboring the T315I mutation with at least 1 prior TKI will be considered for the current study. Previous medical records should be used to confirm the patient's mutational status/history.

The definition of CML-CP will be according to the European Leukemia Network (ELN) criteria ([Hochhaus, 2020](#)), and is outlined below in the inclusion criteria. The investigator or designee must ensure that only patients who meet all the following inclusion and none of the exclusion criteria are offered treatment in the study.

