5.1 Inclusion criteria

Participants eligible for inclusion in this study must meet **all** of the following criteria:

1. Written informed consent must be obtained and signed prior to participation in the study
2. Male or female patients with a diagnosis of CML-CP ≥ 18 years of age
3. Patients must meet all of the following laboratory values at the screening visit:
 - $< 15\%$ blasts in peripheral blood or bone marrow
 - $< 30\%$ blasts plus promyelocytes in peripheral blood or bone marrow
 - $< 20\%$ basophils in the peripheral blood
 - $\geq 50 \times 10^9/L$ ($\geq 50,000/mm^3$) platelets
 - Transient prior therapy related thrombocytopenia ($< 50,000/mm^3$ for ≤ 30 days prior to screening) is acceptable
 - No evidence of extramedullary leukemic involvement, with the exception of hepatosplenomegaly
4. Mutation Analysis testing performed at screening.
5. Prior treatment with a minimum of:
 - 2 prior ATP-site TKIs (i.e. imatinib, nilotinib, bosutinib, dasatinib or ponatinib) in case of absence of T315I mutation
 - 1 prior ATP site TKI (i.e. imatinib, nilotinib, bosutinib, dasatinib or ponatinib) in case of presence of T315I mutation
6. Failure (adapted from the 2020 ELN Recommendations) or intolerance to the most recent TKI therapy at the time of screening
 - Failure for CML-CP patients (CP at the time of initiation of last therapy) is defined as meeting at least one of the following criteria.
 - Three months after the initiation of therapy: $>10\%$ BCR-ABL1 on International Scale (IS) if confirmed within 1-3 months
 - Six months after the initiation of therapy: BCR-ABL1 ratio $> 10\%$ IS
 - Twelve months after initiation of therapy: BCR-ABL1 ratio $> 1\%$ IS
 - At any time after the initiation of therapy, loss of CHR, MR2
 - At any time after the initiation of therapy, the development of new BCR-ABL1 mutations which potentially cause resistance to current treatment
 - At any time 12 months after the initiation of therapy, BCR-ABL1 ratio $\geq 1\%$ IS or loss of MMR
 - At any time after the initiation of therapy, new clonal chromosome abnormalities in Ph+ cells: CCA/Ph+
 - Intolerance is defined as:
 - Non-hematologic intolerance: Patients with grade 3 or 4 toxicity while on therapy, or with persistent grade 2 toxicity, unresponsive to optimal management, including dose adjustments (unless dose reduction is not considered in the best interest of the patient if response is already suboptimal)

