#### **2.8.1.1 Other secondary efficacy endpoints**

**Progression-Free-Survival (PFS)** is defined as time from the first dose of study medication to disease progression to AP/BC or death due to any cause, whichever occurs first during 24,48 and 72 weeks.

For patients without progression, the patient will be censored at the last molecular assessment date the patient was known to be alive and without progression (on or before the cut-off date).

PFS will be analyzed using the Kaplan-Meier Product-Limit method. Patients who do not progress will be censored at the last adequate assessment. Estimates of the 25th, median and 75th percentile of the PFS and their 95% confidence intervals will be provided, if applicable.

**Overall survival (OS)** is defined as the time from the first dose of study medication to death due to any cause during 24, 48 weeks and 72 weeks during study.

If a patient is not known to have died, then OS will be censored at the latest date the patient was known to be alive (on or before the cut-off date). All deaths will be taken into account whatever the death occurred, i.e., even after interruptions, or discontinuation of study medication due to any reason.

OS will be analyzed using the Kaplan-Meier Product-Limit method. Patients who do not progress will be censored at the last adequate assessment. Estimates of the 25th, median and 75th percentile of the OS and their 95% confidence intervals will be provided, if applicable.

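### Platelets of 50 to below 100 x 10⁹/L not attributed to therapy satisfy both chronic-phase entry and the accelerated-phase criterion, so an unchanged entry value can count as a PFS event

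*Protocol*

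**What the plan says.** **Entry.** Protocol 5.1, inclusion 3 (repeated in the protocol summary) requires at screening "≥ 50 x 10⁹/L (≥ 50,000/ mm³) platelets". It sets no condition on cause at or above that floor. Cause appears only in the exception for lower counts: "Transient prior therapy related thrombocytopenia" is accepted for up to 30 days before screening. Section 5 states: "The definition of CML-CP will be according to the European Leukemia Network (ELN) criteria", "and is outlined below in the inclusion criteria".

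**Progression.** Protocol 9.1.1 lists "Accelerated phase (AP) as defined by any of the following". One of the four items is a platelet count below 100 x 10⁹/L "that is unrelated to therapy". The same section says: "In the event of disease progression the patient must be discontinued from the study treatment".

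**PFS.** SAP 2.8.1.1 measures PFS from first dose to "disease progression to AP/BC or death due to any cause", and Protocol 12.5.2.4 agrees. Neither says what to do with a patient who already meets an AP criterion at baseline. The one baseline exclusion that the SAP applies to time-to-event analyses, a note in 2.8.2, concerns molecular response.

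**The concern.** An entry definition of chronic phase and a progression definition of AP should not be true of the same patient on the same day. For platelets they can be. If 9.1.1 is applied as written, a stable count that was acceptable at entry becomes progression, with treatment stopped and a PFS event recorded. If an investigator instead reads progression as implying change, the same patient stays on treatment and is event-free. Nothing in the text chooses between these readings, and Protocol 10.2.3 provides no adjudication committee, so sites could classify identical patients differently.

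The SAP carries a progression call into other endpoints as well. A patient who discontinues before responding is a non-responder (2.8.2). A patient who stops for progression before responding is censored at the longest follow-up in the treatment group, as someone who can no longer respond (2.8.2, 2.8.3). Progression to AP/BC also ends duration of response (SAP 2.8.2 and Protocol 8.4.1, though Protocol 12.5.2.3 omits it).

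**Working it through.** **Step 1: compare the limits** (Protocol 5.1, inclusion 3, against Protocol 9.1.1).

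| Item | Entry | AP | Can both hold? |
|---|---|---|---|
| Blasts | <15% | ≥15% (and <30%) | No |
| Blasts plus promyelocytes | <30% | ≥30% | No |
| Basophils | <20% | ≥20% | No |
| Platelets (x 10⁹/L) | ≥50 | <100, not due to therapy | Yes: 50 to <100, not due to therapy |

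Three of the four AP limits begin exactly where entry ends. Only platelets overlap. Because any one item suffices, the platelet item alone makes the patient AP.

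**Step 2: look for text that removes the overlap.** Section 9.1.1 does not require new onset, worsening from baseline or confirmation. The PFS definitions and the PFS censoring rule (Protocol 12.5.2.4; SAP 2.8.1.1 and 2.8.3) contain no baseline condition. The protocol does not say whether therapy means asciminib alone or also earlier TKIs. A wider meaning shrinks the overlap but does not close it.

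**Step 3: cohort sizes.** The plan gives no PFS assumption to reproduce. Its cohort sizes (Protocol 12.9) do reproduce: 1.96² × 0.18 × 0.82 / 0.12² = 39.4, so 40 evaluable; 40 / 0.90 = 44.4, so 45 for each of Cohorts A and B. Cohort C is set at 25.

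**Step 4: effect of one such patient.** With the whole cohort at risk, one event lowers the Kaplan-Meier estimate by 1/n:
- Cohort A or B: 1/45 = 2.2 points.
- Cohort C: 1/25 = 4.0 points.

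The step is slightly larger if earlier censoring has already reduced the number at risk.

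**Step 5: how many patients.** The documents give no figure. For assumed shares f, the expected number is n × f and the chance of at least one is 1 − (1 − f)ⁿ:

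| Assumed share | Expected, n = 45 | At least one, n = 45 | Expected, n = 25 | At least one, n = 25 |
|---|---|---|---|---|
| 2% | 0.9 | 60% | 0.5 | 40% |
| 5% | 2.25 | 90% | 1.25 | 72% |
| 10% | 4.5 | 99% | 2.5 | 93% |

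The share must satisfy three conditions together: a count in the range, not attributed to therapy, and recorded as AP. These values illustrate scale only and are not estimates.

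**The case against.** The best defence is that the protocol does not rest chronic phase on inclusion 3 alone. Section 5 refers to ELN criteria, and inclusion 2 separately requires a diagnosis of CML-CP, so a patient with disease-related low platelets might be excluded there and inclusion 3 be only a laboratory floor. That reading is possible, but Section 5 points back to the inclusion criteria for the definition, and inclusion 3 admits these patients without qualification. If they were meant to be excluded, the passages still disagree.

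Second, every participant has had at least one prior TKI, and those without T315I at least two. Many counts of 50 to below 100 will be put down to treatment and so fall outside the AP item. This stands, and it limits the number affected.

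Third, progression ordinarily implies change, and the AP item needs a causal assessment by the investigator. This also stands as a sensible reading, but it is not written down.

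Three stronger conclusions that a reader might draw are not supported:
- *Eligible patients would be withdrawn at their first on-study count.* Table 8-1 first schedules progression status at Week 12, with none at Week 1 Day 1, and no rule derives AP automatically from platelet counts.
- *Artefactual events could match the number of true AP/BC events.* The documents forecast neither number. The nearest figure, 38 of 239 (15.9%) discontinuing for progressive disease in the phase I study (Protocol 1.1.2.2), would be about 7 of 45 (0.159 × 45 = 7.2). That population also included ALL patients and is not comparable.
- *Duration of response would be cut short for all such patients.* It is affected only if AP is called after a response; a patient stopped before responding never enters that analysis.

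**Conclusion.** The overlap is real and lies in the current text. Followed literally, it turns an unchanged entry platelet count into progression, with mandatory discontinuation and a PFS event. The size is about 2.2 points per affected patient in Cohort A or B and 4 points in Cohort C. The number affected is unknown and probably small, given the attribution condition.

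The conclusion assumes that 9.1.1 is applied as worded and that at least one patient enters in the range without a therapy-related cause. PFS is a secondary, descriptive endpoint with no hypothesis test, and neither the primary safety endpoint's definition nor the sample size depends on this point. It is worth correcting because the present rule can give a wrong classification and the correction is cheap.

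**What to change.** **Protocol.** Inclusion 3 in 5.1 and the AP platelet item in 9.1.1 must be reconciled, and 9.1.1 should say whether therapy includes prior TKIs. Which threshold is right is a clinical decision, and none is proposed here.

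**SAP.** Add to 2.8.1.1 and 2.8.3 that an AP call is not counted as progression when it rests only on the platelet criterion, that criterion was already met at baseline (as defined in SAP 2.1.1), and the count has not worsened from baseline. Apply the same rule to duration of response and to progression-based censoring in time to response. Add a sensitivity analysis that counts such calls as events.

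The condition on worsening is needed. A rule that ignored the criterion whenever it was met at baseline would also discard a genuine further fall. What counts as worsening should be agreed clinically and written down before database lock. The two documents should change together; otherwise a patient stopped for progression under 9.1.1 would not be a PFS event and the reports would disagree.

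**Cost.** A protocol clarification, a sentence or two in the SAP, a small extra derivation and one more analysis. The platelet counts are already scheduled.

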9.1.2 Withdrawal of informed consent

Participants may voluntarily withdraw consent to participate in the study for any reason at any time. Withdrawal of consent occurs only when a participant:

- Does not want to participate in the study anymore, and
- Does not want any further visits or assessments, and
- Does not want any further study related contacts

In this situation, the investigator should make a reasonable effort (e.g. telephone, e-mail, letter) to understand the primary reason for the participant’s decision to withdraw his/her consent and record this information.

Where consent to the use of personal and coded data is not required, participant therefore cannot withdraw consent. They still retain the right to object to the further use of personal data.

Study treatment must be discontinued and no further assessments conducted, and the data that would have been collected at subsequent visits will be considered missing.

Further attempts to contact the participant are not allowed unless safety findings require communicating or follow-up.

All efforts should be made to complete the assessments prior to study discontinuation. A final evaluation at the time of the participant's study discontinuation should be made as detailed in the assessment table.

Novartis will continue to retain and use all research results (data) that have already been collected for the study evaluation.

9.1.3 Lost to follow-up

For participants whose status is unclear because they fail to appear for study visits without stating an intention to discontinue or withdraw, the investigator must show "due diligence" by documenting in the source documents steps taken to contact the participant, e.g. dates of telephone calls, registered letters, etc. A participant should not be considered as lost to follow-up until due diligence has been completed or until the end of the study.

9.1.4 Early study termination by the sponsor

The study can be terminated by Novartis at any time.

Reasons for early termination:

- Unexpected, significant, or unacceptable safety risk to participants enrolled in the study
- Decision based on recommendations from applicable board(s) after review of safety and efficacy data
- Discontinuation of study drug development

In taking the decision to terminate, Novartis will always consider participant welfare and safety. Should early termination be necessary, participants must be seen by treating physician as soon as possible and treated as a prematurely withdrawn participant. The investigator may be informed of additional procedures to be followed in order to ensure that adequate consideration is given to the protection of the participant's interests. The investigator or sponsor depending on local regulation will be responsible for informing IRBs/IECs of the early termination of the trial.

9.2 Study completion and post-study treatment

The patients are treated in the study up to end of study treatment period defined as up to 72 weeks after the last patient receives the first dose unless patients have discontinued treatment earlier. The end of the study will occur when the last patient enrolled (40 mg BID, 80 mg QD or 200 mg BID cohort) into the study completes 72 weeks of treatment or experience treatment failure.

The primary analysis (cut-off date) is defined as the date when all patients (in Cohort A, B and C) have been on study treatment for 24 weeks ([Section 12](#)) or discontinued earlier. Subsequent to this analysis, the primary clinical study report (CSR) will be developed. Following the cut-off date for the primary CSR, the study will remain open. Patients who are ongoing at the time of the primary analysis will continue to receive the study treatments (asciminib) during the study treatment period as defined above. The end of study treatment analysis will be conducted with a cut-off date 30 days after the end of study treatment period to ensure all available treatment data from all patients in the study is analyzed and summarized in a final CSR.

After the end of the study treatment period the assigned study treatment will be made available to patients who in the opinion of the Investigators are still deriving clinical benefit. This may be outside of this study through alternative options including, but not limited to, an expanded access/compassionate use /managed access program or access to commercial supplies in applicable countries.

10 Safety monitoring and reporting

10.1 Definition of adverse events and reporting requirements

10.1.1 Adverse events

An adverse event is defined as the appearance of (or worsening of any pre-existing) undesirable sign(s), symptom(s), or medical condition(s) that occur after patient's signed informed consent has been obtained.

Adverse events of special interest (AESI) are defined as events (serious or non-serious) which are ones of scientific and medical concern specific to the sponsor's product or program, for which ongoing monitoring and rapid communication by the investigator to the sponsor may be appropriate. Such events may require further investigation in order to characterize and understand them.

Adverse events of special interest are defined on the basis of an ongoing review of the safety data. AESIs are discussed in detail in the [[Asciminib Investigator's Brochure](#)].

Abnormal laboratory values or test results occurring after informed consent constitute adverse events only if they induce clinical signs or symptoms, are considered clinically significant, require therapy (e.g., hematologic abnormality that requires transfusion or hematological stem cell support), or require changes in study medication(s).

Adverse events that begin or worsen after informed consent should be recorded in the Adverse Events eCRF. Conditions that were already present at the time of informed consent should be recorded in the Medical History page of the patient's eCRF. Adverse event monitoring should be continued for at least 30 days (or 5 half-lives, whichever is longer) following the last dose of study treatment. Adverse events (including lab abnormalities that constitute AEs) should be described using a diagnosis whenever possible, rather than individual underlying signs and symptoms. When a clear diagnosis cannot be identified, each sign or symptom should be reported as a separate Adverse Event.

Adverse events will be assessed and graded according to the Common Terminology Criteria for Adverse Events (CTCAE) version 5. Grade 1 to 5 will be used to characterize the severity of the Adverse Event.

If CTCAE grading does not exist for an adverse event, the severity of mild, moderate, severe, and life-threatening, death related to the AE corresponding respectively to Grades 1 - 5, will be used. Information about any deaths (related to an Adverse Event or not) will also be collected through a Death form.

The occurrence of adverse events should be sought by non-directive questioning of the patient (subject) during the screening process after signing informed consent and at each visit during the study. Adverse events also may be detected when they are volunteered by the patient (subject) during the screening process or between visits, or through physical examination, laboratory test, or other assessments. As far as possible, each adverse event should be evaluated to determine:

1. The severity grade (CTCAE Grade 1-5)
2. Its duration (Start and end dates)
3. Its relationship to the study treatment (Reasonable possibility that AE is related: No, Yes)
4. Action taken with respect to study or investigational treatment (none, dose adjusted, temporarily interrupted, permanently discontinued, unknown, not applicable)
5. Whether medication or therapy was given (no concomitant medication/non-drug therapy, concomitant medication/non-drug therapy)
6. Whether it is serious, where a serious adverse event (SAE) is defined as in [Section 10.1.2](#) and which seriousness criteria have been met
7. Outcome (not recovered/not resolved, recovered/resolved, recovering/resolving, recovered/resolved with sequelae, fatal, unknown)

If the event worsens the event should be reported a second time in the eCRF noting the start date when the event worsens in toxicity. For grade 3 and 4 adverse events only, if improvement to a lower grade is determined a new entry for this event should be reported in the eCRF noting the start date when the event improved from having been Grade 3 or Grade 4.

All adverse events should be treated appropriately. If a concomitant medication or non-drug therapy is given, this action should be recorded on the Adverse Event eCRF.

Once an adverse event is detected, it should be followed until its resolution or until it is judged to be permanent, and assessment should be made at each visit (or more frequently, if necessary) of any changes in severity, the suspected relationship to the study treatment, the interventions required to treat it, and the outcome.

Natural progression or deterioration of the malignancy under treatment (including loss of response, progression to accelerated phase or blast crisis and death due to disease progression), will be recorded as part of the efficacy evaluation and should NOT be reported as an AE/SAE.

Signs and symptoms clearly associated with the disease under study should NOT be reported as AEs unless they are newly emergent (i.e. not previously observed in the patient), judged by the Investigator to be unusually severe or accelerated, or if the Investigator considers deterioration of disease-related signs and symptoms to be caused directly by the study drug. If

there is any uncertainty about an AE being due solely to the disease under study, it should be reported as an AE or SAE as appropriate.

